surgery⁴. Recently, there has been increasing interest in the effectiveness of pain control with the use of quadratus lumborum blocks after THA . Currently, case reports have established a precedent regarding the efficacy of the QLB for THA^{5,6,10} in providing superior analgesia and decreasing verbal numerical pain scores, but randomized trials are still lacking. The goal of this study is to compare verbal numerical pain scores, post-operative pain medication (opioid) consumption, physical therapy scores, and patient satisfaction in patients that receive QLB versus no peripheral nerve blockade in patients undergoing THA. The results of this study have the potential to change the standard of care for patients undergoing THA.

b. Describe how outcomes will be measured for this protocol.

The primary end points are as follows:

1. Pain scores (numerical) will be obtained at immediate post op, 24 hours and 48 hours after surgery
2. Pain medication (opioid) use intraoperatively, as well as at 24 hours and 48 hours postoperatively
3. Physical therapist assessment of independence in mobility and transfers
4. Distance ambulated at 24 hours and 48 hours after surgery.

15. Background - in nontechnical, lay language

Summarize in 2-3 paragraphs past experimental and/or clinical findings leading to the design of this protocol. Include any relevant past or current research by the PI. For drug and device studies, summarize the previous results (i.e., Phase I/II or III studies).

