16. Participants (Screening and Selection)

- a. How many participants are to be enrolled at UAB (if other sites relying on UAB IRB, list the number for each site)? **100**
If multi-site study, total number at all sites/institutions: **N/A**
- b. Describe the characteristics of anticipated or planned participants (if multiple groups, repeat list for each group).
Sex: **M,F**
Race/Ethnicity: **any**
Age: **>18 years**
Health status: **American Society of Anesthesiologist (ASA) Physical Status Score 1, II, or III**
- c. From what population(s) will the participants be derived? **All patients scheduled for total hip arthroplasty are scheduled in the preoperative assessment clinic days to weeks prior to their surgery. Study participants will be derived from this population.**

Describe your ability to obtain access to the proposed population that will allow recruitment of the necessary number of participants: **Before total hip arthroplasty, all patients report to the Highlands Preoperative assessment Clinic (HPAC) for standard of care preoperative assessment and examination and preoperative testing, tailored to patient comorbidities. This is not a service that will be billed additionally for study participants, as it is standard of care for all total hip arthroplasty patients, regardless of participation in the study. During this visit they will be given a “Patient Information Sheet,” describing the study. On the day of surgery, patients scheduled for surgery will be seen in the preoperative holding area and enrolled in the study if they choose and are appropriate candidates.**

- d. Describe the inclusion/exclusion criteria:

Inclusion Criteria: Patients undergoing total hip arthroplasty under spinal anesthesia. Adults, 18 years of age or older. Patients classified by the American Society of Anesthesiology (ASA) class I, II, or III.

Exclusion Criteria; Any patient not classified as an ASA I, II, or III. Those who are allergic or intolerable to local anesthetics. Patients with pre-existing neurologic or anatomic deficiency and lower extremity on the side of the surgical site, or patients with coexisting coagulopathy. Patients that are pharmacologically anticoagulated will be excluded if placement of peripheral nerve block would be contraindicated according to ASRA (American Society for Regional Anesthesia) guidelines or if spinal anesthesia would be contraindicated according to ASRA guidelines.

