A. Participants in the study will be randomly assigned to either receive the pain block ("block group") or not ("control group"). The patient will be blinded and thus unaware of the group that they have been assigned. The patients are receiving sedation, including fentanyl and midazolam, an amnestic, prior to ultrasound scanning and +/- block placement. The amnestic properties of sedation will serve as blinding for the procedure. In the postoperative survey, we

ask the patients which group they believe they were in, which will help assess the adequacy of the blinding.

- a. **Block group: Subjects that are in the block group will receive the pain block while they are in pre-operative holding. The block will be administered as follows:**
 - i. **The patient will be placed on their side. Standard of care noninvasive monitors will be used, and oxygen will be given by nasal cannula. Midazolam and fentanyl will be given to patient comfort. Note: midazolam and fentanyl are provided to all patients who are receiving this surgery and is not part of this research project. The timing of the delivery of this medication may differ than standard of care, but the doses and indications are the same. Skin will be prepped and draped as per standard of care.**
 - ii. **Using ultrasound guidance, we will locate the appropriate space for the block. We will first inject numbing medication called lidocaine under the patient's skin (1-2 mL of 1% lidocaine; 10-20 mg). Then, we will inject another numbing medication called bupivacaine (30 mL of 0.25% bupivacaine with 1:400,000 epinephrine; 75 mg bupivacaine and 75 mcg epinephrine) between muscles using a syringe and needle.**
 - iii. **After the block is placed, patients will have their surgery performed.**
- b. **Control group: Patients randomized to the control group will be treated in the same manner (as described in section "i" above) as those randomized to the block group. The ultrasound probe will be used to identify the quadratus lumborum muscle, similar to patients in the block group. However, no local anesthetic will be injected.**

B. Postoperative data will be collected for both groups by a blinded study team member listed on this protocol.

- a. **Post-operative data that will be collected is listed in the attached Case Report Form.**
- b. **Information obtained from the patient will be collected using the attached Patient Interview Script.**
- c. **Patient will be followed up until nerve block resolves.**

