- d. **The hours from block placement until hospital discharge will be calculated.**

b. What is the probable length of time required for the entire protocol (i.e., recruitment through data analysis to study closure)? **One year.**

c. What is the total amount of time each participant will be involved? **Each participant will be involved in the study for approximately 48 hours. Each procedure time period is listed below.**

d. If different phases are involved, what is the duration of each phase in which the participants will be involved? If no phases are involved, enter "None." **None**

e. List the procedures, the length of time the procedure takes, the total # of times the procedure is performed, and indicate whether each is performed solely for research or would already be performed for treatment or diagnostic purposes (routine care) for the population.

-Insert additional table rows as needed.

-If procedure is sometimes research and sometimes routine care, include on separate lines with number of times as each.

Procedure	Length of Time Required of Participants	Frequency of Repetition	Research (Res) – OR- Routine Care
Pre-surgical Evaluation on the day of surgery	30 minutes	once	 Res  Routine
Randomization on day of surgery	5 minutes	Once	 Res  Routine
Placement of block	Approximately 30 min.	Once	 Res  Routine
Post Anesthesia Care Unit (PACU) assessment	10 minutes	Once	 Res  Routine
First postoperative assessment survey (approximately 24 hours after surgery)	10 minutes	Once	 Res  Routine
Second postoperative assessment survey (approximately 48 hours after surgery)	10 minutes	Once	 Res  Routine

- f. Will an interview script or questionnaire be used? Yes No
If Yes, attach a copy.
- g. Will participants incur any costs as a result of their participation? Yes No
If Yes, describe the reason for and amount of each foreseeable cost. _____
- h. Will participants be compensated? Yes No
If Yes, complete i-v.
i. Type: (e.g., cash, check, gift card, merchandise): _____

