General Data Analysis Plan: All demographic and clinical variables with continuous measures will be expressed as means and standard deviations; categorical factors will be expressed as proportions. For non-normal data, the medians and inter quartile ranges will be displayed. The distribution of the continuous factors will be examined using the Kolmogorov-Smirnov test. For data that are normally distributed, the one-way ANOVA and Student's t-test will be used to compare groups of data. For data that are not normally distributed, the Kruskal-Wallis and Mann-Whitney tests will be used for comparisons. Chi-square and Fisher's exact tests will be used to analyze categorical data. For all comparisons, a value of $p < 0.05$ will be considered statistically significant.

Primary Outcome Analysis: Statistical analyses will be performed using SAS for Windows, version 9.2. Student's t-test will be used to compare post-operative pain scores for investigational and control subjects. Linear regression will be also be used to test the relationship between pain scores and regional anesthetic technique, while controlling for relevant clinical and demographic variables. Distance of first ambulation will be analyzed using Cox proportional-hazards model. Student's t-test will be used to compare patient and surgeon satisfaction.

Statistical Power and Sample Size Estimates : Sample size (50 each group) was determined using a Cohen's d table assuming a mean pain VAS score of 8 (SD = 3) on a scale of 0-10 for control subjects. A difference of VAS score of 3 between two study groups will be clinically relevant. A sample of 100 participants (50 patients per group) will have approximately 95% power to detect a reduction in pain score difference of 3 with significance level alpha of 0.05. We will perform an interim analysis after 50 patients have completed the study (25 patients in each group).

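### Two primary end points measure mobility, but no preoperative mobility value is listed and covariate adjustment is stated for pain only: the comparison stays valid but gives up precision

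*Combined protocol and SAP*

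**What the plan says.** Item 14.b introduces four outcomes with "The primary end points are as follows". The third is "Physical therapist assessment of independence in mobility and transfers" and the fourth is "Distance ambulated at 24 hours and 48 hours after surgery", so two of the four are mobility measures taken after surgery.

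No preoperative counterpart appears in the supplied text. The procedure table in item 17.e has a line for "Pre-surgical Evaluation on the day of surgery", marked as routine care, without saying what is measured. Item 16.c describes an earlier clinic visit "for standard of care preoperative assessment and examination and preoperative testing, tailored to patient comorbidities", also without naming a mobility measure. Item 17 states that "Post-operative data that will be collected is listed in the attached Case Report Form"; that form is an attachment and was not available.

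Item 16.e gives 1:1 allocation by random number generator and describes no stratification.

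Under Primary Outcome Analysis, a linear regression is planned to "test the relationship between pain scores and regional anesthetic technique, while controlling for relevant clinical and demographic variables". That is the only mention of covariates. Distance at first ambulation is assigned a Cox model with no covariates named. The therapist's rating has no specific analysis and falls back on the unadjusted tests of the General Data Analysis Plan.

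**The concern.** How well a patient walked and transferred before surgery is a natural predictor of how well they do so one and two days afterwards. It is fixed before randomization and is therefore a legitimate covariate. The plan accepts adjustment in principle for pain, but does not extend it to the two end points where preoperative function is most obviously relevant.

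Two things are at stake. Between-patient variation that a baseline value could explain stays in the error term, which widens the intervals for both mobility end points. And if the arms happen to differ in prior walking ability, nothing in the listed data would reveal it or allow a correction. The value has to refer to the time before randomization, so it is best captured then.

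**Working it through.** **The plan's own figure.** The only stated power is about 95%, for a 3-point pain difference with SD 3, 50 per group and alpha 0.05. The normal approximation (two-sided) gives Φ(3/(3 × √(2/50)) − 1.96) = Φ(5.00 − 1.96) = 99.9%, so the figure does not reproduce. That is a separate matter, in the conservative direction. It concerns pain and says nothing about power for mobility, for which the documents give no SD, effect size or power.

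**Inputs.** 50 per group comes from the Statistical Considerations. The baseline-outcome correlation r is assumed and shown from 0.1 to 0.6. A true effect of 0.5 SD is assumed for illustration only.

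**Step 1: size of chance imbalance.** The SE of the standardized baseline difference is √(2/50) = 0.20, so its 95% range is ±1.96 × 0.20 = ±0.39 SD. The chance of an imbalance above 0.2 SD is 32%, and above 0.3 SD 13%. An imbalance at the 95% limit shifts the unadjusted outcome difference by 0.392 × r SD.

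**Step 2: precision.** In a linear model, adjustment multiplies the variance by 1 − r², so 100 adjusted patients carry the information of 100/(1 − r²) unadjusted ones. Power is for a two-sided t-test with standardized effect 0.5/√(1 − r²); unadjusted it is 69.7%.

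| r (assumed) | 1 − r² | Equivalent N | Shift at 95% limit (SD) | Power at 0.5 SD |
|---|---|---|---|---|
| 0.1 | 0.99 | 101 | 0.04 | 70.1% |
| 0.2 | 0.96 | 104 | 0.08 | 71.4% |
| 0.3 | 0.91 | 110 | 0.12 | 73.7% |
| 0.5 | 0.75 | 133 | 0.20 | 81.6% |
| 0.6 | 0.64 | 156 | 0.24 | 87.2% |

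Estimating one covariate coefficient costs an expected variance factor of about 1 + 1/(100 − 4) = 1.010. At r = 0.1 the net factor is 0.99 × 1.010 = 1.000, so nothing is gained. From r = 0.3 upwards this cost is small beside the gain.

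**Step 3: validity of the unadjusted test.** In 40,000 simulated trials with no treatment effect, the unadjusted t-test rejected in 5.0% at r = 0.3 and at r = 0.5, and the mean difference was zero to within 0.002 SD. Among the 13% of trials with a baseline imbalance above 0.3 SD, the rejection rate was 7.7% (r = 0.3) and 12.7% (r = 0.5). The problem is therefore conditional on an unlucky allocation and averages out over allocations.

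**The case against.** The strongest reply is that nothing is broken. Randomization makes the unadjusted comparison valid, and its confidence interval already allows for chance imbalance. This stands. A reader might infer that the mobility results would be biased or the type I error inflated; Step 3 shows neither.

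Second, the gain is hypothetical. The documents offer no correlation, and a coarse baseline such as walking aid may correlate weakly with distance walked. This also stands, which is why the range starts at 0.1, where the gain vanishes. The 0.5 SD effect is equally an assumption.

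Third, the arithmetic belongs to a linear model, whereas the plan names a Cox model for distance and a graded rating may need an ordinal one. In those models the gain does not follow 1 − r² exactly, and adjustment changes the estimand, because hazard and odds ratios are non-collapsible. A Cox model can also carry covariates; the plan is silent on them rather than excluding them.

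Fourth, a reader might infer that no mobility baseline is collected, or that the trial admits every level of walking ability. Neither can be claimed. The Case Report Form is cited for postoperative data but was not seen, and could hold such an item. Item 16.d excludes patients with a prior neurologic or anatomic deficiency of the operated limb, which narrows the spread without removing it.

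What survives is that the supplied text lists no baseline mobility value and that the stated adjustment stops at pain. The second part holds whatever the form contains.

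**Conclusion.** The point holds as a missed gain in precision, together with the inability to correct a chance imbalance in prior walking ability from the data the plan lists. It does not hold as a claim of bias or of an invalid test.

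The size depends on a correlation the documents do not give: negligible at r = 0.1 to 0.2, modest at 0.3, material at 0.5 to 0.6. This rests on 50 per group, a continuous outcome and a linear model, so it is an order of magnitude for Cox or ordinal analyses. It would be too strong to say that the trial forgoes 10 to 56 patients' worth of information: that range takes r = 0.3 to 0.6 for granted and borrows a model the plan does not use. The case for acting is that the remedy is cheap and no power is shown for the mobility end points.

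**What to change.** Unless the Case Report Form already does so, record usual walking aid and independence in walking and in transfers, in the holding area, after consent and before randomization. The earlier clinic visit is less suitable for a research question, because item 16.c places enrollment on the day of surgery.

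In the Primary Outcome Analysis, pre-specify this value as a covariate in one primary model per mobility end point, and name the adjusted estimate as the result:

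- Distance at 24 and 48 hours: a linear regression, or a rank-based one if distances are skewed, that replaces the Cox model so that distance does not have two competing analyses. If the Cox model is kept, add the covariate to it.
- Therapist's rating: an ordinal or linear model, according to the scale used, which the protocol should state.

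No further covariate is needed for this purpose.

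The cost is one or two questions, one field on the form, a short addition to the analysis text and a few degrees of freedom. With an ordinal or Cox model, the adjusted effect is conditional on the covariate and should be reported as such.

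### Sedation amnesia does not conceal the block arm's flank puncture, and a group guess asked after pain has been felt mixes lost blinding with efficacy

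*Combined protocol and SAP*

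**What the plan says.** Item 17.A says patients are unaware of their group and names the mechanism: "The amnestic properties of sedation will serve as blinding for the procedure". Sedation is not set to a fixed level: "Midazolam and fentanyl will be given to patient comfort". No check of amnesia is described.

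Step i (lateral position, monitors, oxygen, sedation, skin preparation, draping) applies to both arms, and both have an ultrasound scan. Step ii belongs to the block arm alone: "We will first inject numbing medication called lidocaine under the patient's skin", followed by the 30 mL bupivacaine injection "between muscles using a syringe and needle". The control paragraph ends: "However, no local anesthetic will be injected". No matched puncture, dressing or other masking of the site is described. Item 16.d limits enrolment to surgery under spinal anesthesia, so a spinal is common to both arms.

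On assessment, Item 17.B states: "Postoperative data will be collected for both groups by a blinded study team member listed on this protocol". In the postoperative survey the team will "ask the patients which group they believe they were in". The table in Item 17.e lists a PACU assessment and two surveys, at about 24 and 48 hours, and does not say which one carries the guess. The Statistical Considerations section plans no analysis of it.

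**The concern.** Pain score is the first end point in Item 14.b and is reported by the patient. Satisfaction is too, and opioid use and ambulation depend partly on what the patient feels and expects. A patient who works out the allocation may report accordingly, most plausibly in favour of the block.

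Amnesia acts on memory of the procedure. It does nothing about evidence that remains on the skin afterwards, which the patient or the person collecting outcomes might notice. Item 17.B.c also provides for follow-up until the block resolves, an event that exists in one arm only, without saying who does it.

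The planned check is hard to read. By 24 or 48 hours a patient with little pain has reason to guess block because the block worked. A high rate of correct guesses could then mean failed blinding, an effective block, or both.

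**Working it through.** **1. What differs between arms (Items 16.d and 17.A)**

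| Element | Block | Control |
|---|---|---|
| Position, monitors, oxygen, sedation, preparation, draping | yes | yes |
| Ultrasound scan | yes | yes |
| Spinal anesthesia | yes | yes |
| Skin lidocaine at block site | yes | not described |
| Block needle, 30 mL injection | yes | no local anesthetic injected |
| Masking of the site afterwards | not described | not described |

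The difference is confined to the block site, taken here to be the flank.

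**2. Inputs.** From Statistical Considerations: SD 3, difference 3, 50 per arm, alpha 0.05. Sidedness is not stated; two-sided is assumed.

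**3. The plan's own figure.** SE = 3 × √(2/50) = 0.6, and the noncentrality is 3/0.6 = 5. Two-sided t-test power is 99.9%, not the stated 95% or so; about 27 per arm would give 95%. The misstatement is conservative and does not bear on blinding.

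**4. The guess under perfect blinding.** Assume normal scores with equal SD, and that each patient guesses block when pain falls below the midpoint of the two arm means. Normality is only approximate for a control mean of 8 with SD 3 on a 0-10 scale.

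- Probability of a correct guess in each arm: p = Φ(effect / (2 × SD)).
- At the planned effect: Φ(3/6) = Φ(0.5) = 0.69.
- Per-arm blinding index: 2p − 1 (0 means chance guessing).

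| True effect (points) | Correct guesses | Index | Chance that guess-by-arm test gives p<0.05, 50 per arm |
|---|---|---|---|
| 0 | 50% | 0 | 5% |
| 1 | 57% | 0.13 | 26% |
| 2 | 63% | 0.26 | 75% |
| 3 | 69% | 0.38 | 98% |

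If patients guess this way, a blinding check that appears to fail is the expected result of a block that works as planned.

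**5. What a reporting bias would do (illustration).** Let b be the net shift in reported pain between arms with no true effect. Roughly, b = share unblinded × expectation effect in points. Neither factor is in the documents; for example, 0.5 × 1 = 0.5 and 0.5 × 2 = 1.0. The noncentrality is b/0.6. The smallest significant observed difference is 1.984 × 0.6 = 1.19 points.

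| b (points) | b/0.6 | p<0.05 |
|---|---|---|
| 0.5 | 0.83 | 13% |
| 0.75 | 1.25 | 24% |
| 1.0 | 1.67 | 38% |

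The nominal rate is 5%.

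**The case against.** The blinding is more careful than a bare contrast of needle against scan suggests, and several stronger readings do not hold.

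- A reader might infer that only block patients are punctured. All patients have spinal anesthesia, so recalling or feeling a needle in the back does not reveal the allocation. Only the block site differs.
- A reader might infer that the puncture will be seen. No passage mentions a visible mark, and nothing has the data collector inspect the site. Visibility is a reasonable inference, not a stated fact.
- A reader might infer that the guess can never separate unblinding from efficacy. The Patient Interview Script and Case Report Form are attachments not included here, and a question on the reason for the guess may already exist.
- A reader might infer that a sham injection was considered and turned down. The documents do not discuss one.

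The bias figures rest on chosen values. A net bias of 1 point would also very rarely produce the 3-point difference that the plan calls clinically relevant: (3 − 1)/0.6 = 3.33, a probability of about 0.0004. The risk is a false significant result, not a false large one.

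An earlier guess is not a clean remedy either. The block precedes surgery and immediate postoperative pain is itself an end point, so a PACU guess also follows onset of any effect, and an index computed from it carries the same confounding. The recorded reason does most of the separating.

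What stands is that nothing described masks the site, the planned guess follows the pain experience, and no analysis of it is specified.

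**Conclusion.** The point holds as a cheap improvement to partial blinding; the documents do not show that blinding is absent or will fail. Sedation amnesia and matched preparation address what patients remember. They do not address a puncture site noticed later by the patient or the blinded collector. The guess as placed would be correct about 69% of the time at the planned effect even if blinding were perfect, given normal scores and guessing from pain alone. The false-positive rates of 13%, 24% and 38% show how sensitive the primary test is to assumed biases of 0.5, 0.75 and 1.0 points; they do not estimate the bias in this trial.

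**What to change.** In Item 17.A, apply the same opaque dressing over the scanned flank site in both arms. Keep it on until the 48-hour assessment, or until discharge if that comes first. Have any site check made by staff who do not collect outcomes.

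At the existing PACU assessment, after the pain score, add a group guess and its reason. Keep the later guess as a second reading. In Statistical Considerations, state that guesses will be reported by arm and by reason (saw or remembered the procedure, or inferred it from pain), with a per-arm blinding index beside the pain result. If the interview script already asks for a reason, only the timing and the reporting need adding.

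The cost is one dressing per patient and one short question. There are three downsides:

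- The site is covered between checks, which matters because Item 19.a lists bleeding and infection as risks.
- Masking ends early for patients discharged before 48 hours.
- Some patients may be drowsy in PACU.

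The change lessens the confounding of lost blinding with efficacy; it does not remove it.

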Currently, regional anesthesia techniques for total hip arthroplasty are limited. Fascia iliaca blocks (nerve blocks between the muscles of the hips) have been employed to provide analgesia for hip surgeries with blockade of the femoral, lateral femoral cutaneous, and obturator nerves via injection of local anesthetic in the iliacus fascia. In addition, lumbar plexus blocks have also been employed for post-operative analgesia, but the complexity of the block is high, and complications including epidural anesthesia are not infrequent. The quadratus lumborum block (QLB) is an abdominal truncal block in which local anesthetic is deposited into the thoracolumbar fascia (area between the muscle) or the quadratus lumborum muscle itself with the goal of providing analgesia to the ipsilateral T6 – L1 sensory dermatomes. It has already been demonstrated to provide effective post-operative analgesia for certain abdominal and pelvic surgeries⁷, but its use in total hip arthroplasty is limited to case reports.

The block is accomplished by locating the quadratus lumborum muscle, using a ultrasound probe. Local anesthetic is then injected. Cadaveric studies⁸ have demonstrated dye spread to the lumbar nerve roots and nerves within the transversus abdominis plane (TAP). Carney et al⁹ described a “posterior TAP” block, now known to be synonymous with QLB, that demonstrated contrast spread to the thoracic paravertebral space from T5-L1. Case reports have described analgesia in the corresponding sensory dermatomes after QLB⁴, and have demonstrated efficacy in patient undergoing THA^{5,6,10}. The QLB block has potential to cover lateral femoral cutaneous nerve, femoral nerve, obturator nerve and portions of lumbar plexus.

This study has been designed to investigate the efficacy of the QLB in providing post-operative pain control patients undergoing THA. Previous trials have demonstrated the effectiveness of the block for abdominal and pelvic surgeries, and case reports have shown its applicability in hip arthroplasty. In this randomized, controlled study we aim to compare QLB (block group) with control (control group) in patients undergoing THA with regard to verbal numeric pain scores (to be obtained when patient arrives to PACU & at discharge from PACU, then at 24 and 48 hours after surgery). The duration of analgesia, time to first opioid medication, physical therapy evaluations, time to discharge, and patient satisfaction scores will also be obtained.

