ii. Amount or Value: _____
iii. Method (e.g., mail, at visit): _____
iv. Timing of Payments: (e.g., every visit, each month): _____
v. Maximum Amount of Compensation per Participant: _____

18. Benefits

Describe the potential benefits of the research. **Effective post-operative pain control with regional analgesia can reduce the amount of opioid medications needed perioperatively and therefore, may help participation in physiotherapy, leading to more effective rehabilitation and shorter times to discharge from the hospital. Additionally, greater perioperative pain control can enhance patients' perioperative satisfaction.**

19. Risks - in nontechnical, lay language

- a. List the known risks for participants as a result of participation in the research. This should not include the minimal risk of loss of confidentiality. However, it should include any physical, psychological, social, economic, and/or legal risks. If there is a greater than minimal risk of loss of confidentiality describe why this is so. Do not list risks associated with the standard-of-care procedures.

NOTE: Risks included here should be included in the consent form or information sheet, as applicable.

Assessment of Level of Risk: Minimal risk. Participants in this study have the risk associated with peripheral nerve block including pain and discomfort from the procedure, excessive bleeding, infection, nerve damage and failed analgesia. THA is done at this institution currently either with or without QLB. The study would scientifically compare the two existing methods of perioperative pain control (with or without QLB) to each other.

Risks Associated with 0.25 % Bupivacaine with 1:400,000 epinephrine

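### Does starting the discharge clock at block placement leave the control group without a valid start time?

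*Combined protocol and SAP*

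**What the plan says.** Item 17.B of the protocol opens with: "Postoperative data will be collected for both groups by a blinded study team member listed on this protocol". Sub-item d then defines the discharge measure: "The hours from block placement until hospital discharge will be calculated".

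Item 17.A describes sedation given "prior to ultrasound scanning and +/- block placement", so the scan is for everyone and the block for some. Controls are handled as the block group is, including the ultrasound view of the muscle, but "However, no local anesthetic will be injected".

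On follow-up, Item 17.B.c says: "Patient will be followed up until nerve block resolves". Item 17.c says: "Each participant will be involved in the study for approximately 48 hours".

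The Background (Item 15) lists the measure among others: "The duration of analgesia, time to first opioid medication, physical therapy evaluations, time to discharge, and patient satisfaction scores will also be obtained". The Benefits section (Item 18) hopes for better physiotherapy, "leading to more effective rehabilitation and shorter times to discharge from the hospital". The primary end points in Item 14.b do not include time to discharge, and Statistical Considerations names no analysis for it. Item 17.B.a refers to an attached Case Report Form for the data items; that form is not part of the text under review.

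**The concern.** Read literally, block placement is an event that only one group has. Item 17.A itself separates the scan from the block, so a control has no block time to enter, and no sentence says what stands in for it. If the control clock started at a later event, the block group's hours would include time that the control group's hours leave out. The comparison would then be biased against the block on an outcome the protocol hopes to improve. Such a bias is systematic, so more patients would not remove it.

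The follow-up wording raises a similar doubt. Resolution of a nerve block means nothing for a patient who had none, and an open-ended follow-up sits beside a participation period of about 48 hours with no sentence linking the two.

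**Working it through.** The plan gives no figure for time to discharge, so there is none to reproduce. The check has two parts: which start times the text supports, and how much a mismatch among them could matter.

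**Reading the text**

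1. Item 17.B.d names one start event and applies it under a heading for both groups. It does not ask for a different clock in each group.
2. Item 17.A.b takes controls through the same sedation, positioning and scan, so they have a step that corresponds to the block.
3. The procedure table in Item 17.e lists placement of the block once, at about 30 minutes, in a single schedule for participants. There is no separate control row. The step can be read as one that both groups pass through, with or without injection.
4. Item 17.B has a blinded team member collect the data. Someone who does not know the allocation cannot systematically choose one clock for controls and another for block patients.

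**Size of a mismatch**

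Inputs from the documents: 50 per group (Statistical Considerations) and about 30 minutes for the block step (Item 17.e). The standard deviation of time to discharge is not given; 12 to 24 hours is assumed, with 6 hours as a stricter check.

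Standard error of a difference in means = SD × √(2/50) = 0.2 × SD:

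- SD 6 h: 1.2 h
- SD 12 h: 2.4 h
- SD 24 h: 4.8 h

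If both groups are timed from the same point of the scan/block step, the mismatch is about 0 h and the two-sided test keeps its 5.0%.

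If one group is timed from the start of the step and the other from its end, the mismatch is about 0.5 h. The rejection rates below come from the noncentral t distribution with 98 degrees of freedom and no true difference:

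| SD (h) | Mismatch / SE | Two-sided rejection |
|---|---|---|
| 6 | 0.5/1.2 = 0.42 | 7.0% |
| 12 | 0.5/2.4 = 0.21 | 5.5% |
| 24 | 0.5/4.8 = 0.10 | 5.1% |

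The direction depends on which group is timed from the later point. A later control start counts against the block, and a later block-group start counts in its favour.

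A large effect needs a start time from elsewhere. Suppose controls were timed from the end of surgery and block patients from the start of the block, with an assumed 1.5 to 3 h between the end of the block step and the end of surgery. The mismatch is then 0.5 + 1.5 = 2 h to 0.5 + 3 = 3.5 h. That is 2/4.8 = 0.42 to 3.5/2.4 = 1.46 standard errors. The chance of a significant result against the block would rise from 2.5% to between 6.1% and 30.3%. The arithmetic is right, but nothing in the documents proposes this control clock, and both the interval and the SD are assumed.

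**Follow-up**

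Items 17.B.c and 17.c conflict only if a block outlasts 48 hours, which the documents do not suggest. Item 15 fixes the pain scores at PACU arrival and discharge and at 24 and 48 hours, and Item 14.b fixes postoperative opioid use at 24 and 48 hours. The last survey in Item 17.e is at about 48 hours. These points are the same in both groups, whenever a block wears off. Following a block to resolution serves safety and the duration of analgesia, which concern the patients who had one.

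**The case for a change.** The strongest case for a change is that the protocol's own phrasing makes the block the step that controls do not get. A person filling in a control's record, or an unblinded analyst computing the hours later, must therefore choose a start. Naming one shared event would take a line, whereas a wrong choice could not be cured by a larger sample. The blinded collector is only a partial answer if the calculation is done after allocation is known.

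It stands that the start event for controls is not written down in the text reviewed, and that the Case Report Form cannot be relied on to supply it because its content is unknown. It does not follow that the plan leads to a wrong result. The analyst in this example would find a scan done on every control at the matching moment. Passing over it for a later event, and only in one group, would be the less natural choice. A possible hint of allocation from a field label on the form is speculation about a document not seen, and carries no weight.

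**Conclusion.** No change is needed. This is an undefined term on an additional, non-primary measure with no stated analysis, and analysts would fill it sensibly from a step both groups undergo. Under the readings closest to the text, the mismatch is 0 to about 0.5 h. That is at most 0.21 standard errors if the standard deviation is 12 to 24 h, and 0.42 if it is as small as 6 h. No sample size, power or significance level in the plan depends on it.

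The conclusion rests on the scan/block step serving as the start in both groups. It would fail only if the Case Report Form set a different clock for each group, and nothing in the documents points that way. The follow-up statements are loosely worded but compatible.
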